The proposed research aims to address key questions about the efficacy of MDFT, adapted for use within the UK using a mixed method, two-arm, prospective, individually randomised controlled trial comparing MDFT versus business as usual (BAU). The trial will have an embedded internal pilot to address key questions regarding the parameters for a definitive efficacy study and a concurrent implementation and process evaluation addressing important questions regarding the MDFT intervention in detail.

Intervention

Delivery of MDFT will occur between July 2025 and July 2027. MDFT aims to reduce substance use, improve behavioural issues and reduce young people's involvement in the criminal justice system through multidimensional family therapy. Greater detail on the theoretical framework is available here https://www.mdft.org and a theory of change diagram and narrative provided in figure 2 and appendix I. It is delivered by a qualified MDFT therapist, and it intervenes in four connected areas: (i) the young person, (ii) the parents, (iii) the family, and (iv) the community. The main activities that drive behavioural change are (i) individual therapy sessions between the therapist and young person (typically 8-20 individual sessions), (ii) parent sessions between the therapist and parents (typically 4-10 sessions), (iii) family sessions where the therapist facilitates meaningful conversations among the family members who attend (typically 4-10 sessions), and (iv) sessions between the family and social systems in their community (typically 4-10 community sessions/meetings). Additional activities outside of the session promote individual change, and phone calls to the young person and parents support the development of problem-solving skills for when difficulties in relationships arise.

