On completion of assessment battery research staff receive automated message of a referral, randomisation conduct, allocation relayed back to Barnardo's staff who either initiate MDFT or make referral to BAU.

Randomised to BAU (200) Randomised to MDFT (200)

YP referred to alternative service YP allocated MDFT therapist

Outcome assessment at month 6 Outcome assessment at month 6 (n=182) (n=182)

Outcome assessment at month 12 Outcome assessment at month 12 (n=160) (n=160)

Data is collected at 6- and 12-months using bespoke, secure, on-line data collection system and transferred to secure servers managed by the University of Kent. Six- and 12-month data collection is completed by research staff blind to participant allocation and participants receive a payment of £25 for completing assessments at baseline 6- & 12 months.

Sample size calculations

Sample size estimation was conducted in STATA18. A clinically important effect size for substance use frequency in adolescents is estimated as 0.27, similar to the lower bound

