estimates found in systematic reviews of MDFT (Filges T. et al., 2018, van der Pol et al., 2017b). This equates to a number needed to treat of 6, where at least one in six participants receiving MDFT would show clinically important benefits, and a difference in the frequency of substance use of at least 13% in the MDFT group. Detecting an effect size smaller than this provides no additional benefit, the commissioning of services in England and Wales requires the service to achieve a clinically important difference for the target population. To detect this difference, with power at 80% and alpha of 0.05 and a two-tailed test, requires a sample of 480 participants followed-up at the 6-month endpoint. Using data from other studies of substance using adolescents (Coulton S et al., 2023, Deluca et al., 2020) we estimate the prepost-test correlation of the frequency of substance use to be 0.4, and incorporating this into the sample size calculation reduces the number followed-up to 364, 182 in each group. Assuming a loss to follow-up at the endpoint of 10%, similar to other studies in adolescent substance use populations (Coulton et al., 2024) inflates the number needed to randomise to 400. Assuming 80% of those eligible will be willing to consent an indication of acceptability of the study to participants and a lower figure than other studies in similar populations (Coulton et al., 2024) would mean we would need to approach 480 across both sites. Recruitment will be continuous between September 2025 and January 2027, 28 per month will need to be approached in total across both sites per month with the expectation that 24 will consent to participate in the trial across both sites. We anticipate. Based on relative population size that 40% of referrals will come from Newport and 60% from Bristol.

Table 2: Recruitment/ retention table

	Q1	Q2	Q3	Q4	Q5	Q6	Q7	Q8	Q9	Q10	Q11
Months (e.g. Oct-Dec 23):	May-Jul 25	Aug-Oct 25	Nov 25 - Jan 26	Feb - Apr 26	May-Jul 26	Aug-Oct 26	Nov 26 - Jan 27	Feb - Apr 27	May-Jul 27	Aug-Oct 27	Nov 27 - Jan 28
Target number of children and young people referred into the project	0	50	75	75	75	75	75	75	218	360	500
Target number of children and young people recruited to the project and evaluation	0	40	60	60	60	60	60	60	174	288	400
Target number of children and young people who withdraw/drop out	0	4	6	6	6	6	6	6	23	35	40

Table 3: Sample size calculations

		PARAMETER		
Minimum Detectable Effect Size (MDES)		0.27		

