Sites may drop out of the study due to changes locally related to financial issues or leadership.	All sites have a track record of commitment to the delivery of services and an understanding of research. Senior sign off has been secured at all sites and commitment made to deliver the research as planned.
Imposition of COVID, or similar, restrictions	Both the delivery team and research team have contingency plans for remote working.
Poor quality delivery of MDFT	Fidelity and quality assurance are monitored throughout the study through the MDFT portal. Therapists are supervised both on-site and by staff from MDFT international. Regular

	reports relating to fidelity on the part of the therapist, adherence on the part of participants and quality assurance are made available and reviewed. Issues can be identified quickly and remedial action taken.
Participants do not complete questionnaires because they are too long	The outcome battery has been used in similar populations and takes on average 15 minutes to complete at baseline and 25 minutes at follow up. Response from other studies suggest burden will not be an issue.

Timeline

05/25 - 09/25: Adapt MDFT for delivery in UK, trial set-up, ethics, registration, recruitment of supervisors and therapists.

09/25 – 12/25: Conduct internal pilot with 60 participants recruited.

06/26: Evaluate transition criteria and submit transition report form.

07/26 - 05/27: Recruit 340 to efficacy study.

01/27 – 11/27: Conduct efficacy 6-month follow-up.

07/27 – 05/28: Conduct efficacy 12-month follow-up.

06/28: Analyse results.

09/28: Submit final report

Bibliography

- BALDWIN, S. A., CHRISTIAN, S., BERKELJON, A. & SHADISH, W. R. 2012. The effects of family therapies for adolescent delinquency and substance abuse: a meta-analysis. *J Marital Fam Ther*, 38, 281-304.
- BLACK, C. 2020. review of Drugs evidence relating to drug use, supply and effects, including current trends and future risks. London: HMSO.

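### The approach target of 480 should be 500 at 80% consent, and the recruitment calendars conflict with each other and, in places, with the MDFT delivery end date

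*Protocol*

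**What the plan says.** The Protocol sets out recruitment in three places.

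- **Sample size calculations.** The number to randomise is 400. Assuming 80% of eligible young people consent, this "would mean we would need to approach 480 across both sites". The section continues: "Recruitment will be continuous between September 2025 and January 2027, 28 per month will need to be approached", with 24 per month expected to consent.
- **Table 2.** The row "Target number of children and young people recruited to the project and evaluation" runs 0, 40, then 60 in each of six quarters, then 174, 288 and 400, from May-Jul 2025 to Nov 2027-Jan 2028. The referral row runs 0, 50, six entries of 75, then 218, 360 and 500. The withdrawal row runs 0, 4, six entries of 6, then 23, 35 and 40. The table does not say whether entries are quarterly or cumulative.
- **Timeline.** The internal pilot recruits 60 between September and December 2025, and transition is evaluated in June 2026. Then: "07/26 - 05/27: Recruit 340 to efficacy study".

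On therapy, the Intervention section says "Delivery of MDFT will occur between July 2025 and July 2027" and describes work with a family as typically lasting 4 to 6 months. Appendix I gives a minimum dosage of 12 sessions over 4 months.

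The sample size section also says that, before any adjustment for baseline correlation, the design "requires a sample of 480 participants followed-up at the 6-month endpoint".

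**The concern.** The approach number does not follow from the consent rate beside it, and the monthly figures inherit the error. A site that meets its approach target at the assumed consent rate would under-recruit.

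The calendars differ in end date, in monthly rate, and in whether recruitment pauses after the pilot. This affects more than staffing. Delivery has a stated end date, so the last randomisation date decides how many of the MDFT arm can finish a typical course. The Efficacy study analysis section keeps everyone in their allocated group. MDFT participants who run out of delivery time would therefore remain in the intention-to-treat comparison and pull the estimate towards zero. They could also fail the compliance thresholds planned for the CACE analysis.

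**Working it through.** **Inputs (Protocol, Sample size calculations, unless stated).** Effect size 0.27; two-sided alpha 0.05; power 80%; pre-post correlation 0.4; equal allocation (Randomisation); 10% loss; 400 randomised; 80% consent; September 2025 to January 2027 = 17 months inclusive.

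**1. The plan's own sample size.**
- Unadjusted, per arm: 2 × (1.96 + 0.8416)² / 0.27² = 215.3, so 216 per arm and 432 in total (434 with the t distribution).
- Adjusted: 215.3 × (1 − 0.4²) = 215.3 × 0.84 = 180.9, so 181 per arm and 362 in total. The stated 364 reproduces within rounding.
- The stated 480 followed up before adjustment does not reproduce. It equals 432/0.9, which is a number randomised. The 364 does not depend on it.

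**2. Approach number.**
- Required: 400/0.80 = 500. The stated 480 equals 400 × 1.2.
- The stated monthly rates follow from 480 and 400: 480/17 = 28.2 and 400/17 = 23.5.
- Implied consent: 400/480 = 83.3% and 24/28 = 85.7%. Neither is 80%.
- At 80%, 28 approached gives 28 × 0.8 = 22.4 per month, not 24.
- Correct rate over 17 months: 500/17 = 29.4 per month.

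**3. Effect on power.** Power = Φ(0.27 / √0.84 × √(n/2) − 1.96), where n is the number followed up per arm.

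| Basis | Randomised | Followed up (× 0.9) | Power |
|---|---|---|---|
| Plan's analysed number | – | 364 | 80.2% |
| 400 randomised | 400 | 360 | 79.8% |
| 480 × 0.8 | 384 | 345.6 | 78.2% |
| 28 × 17 × 0.8 | 381 | 342.9 | 77.9% |

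**4. The calendars side by side.**

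| Source | Pattern | Reaches 400 |
|---|---|---|
| Sample size text | Continuous, 24 per month | January 2027 |
| Timeline | 60, no recruitment listed January to June 2026, then 340/11 = 30.9 per month | May 2027 |
| Table 2, quarterly | 40 + 6 × 60 = 400 | Feb-Apr 2027, then lists 174, 288 and 400 more (row total 1,262) |
| Table 2, cumulative | Stays at 60 until April 2027 | Nov 2027-Jan 2028 |

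**5. Against the delivery window.** This assumes even accrual, 1:1 allocation and delivery to the end of July 2027.
- Text: a January 2027 end leaves about 6 months for the last entrant.
- Timeline, February to May 2027: 30.9 × 4 = 123.6 entrants, about 62 in the MDFT arm (62/200 = 31%), with less than about 6 months left.
- Of these, April to May 2027: 30.9 × 2 = 61.8 entrants, about 31 in the MDFT arm, with less than about 4 months left.
- Table 2, quarterly to 400: 60 entrants in Feb-Apr 2027, about 30 in the MDFT arm, with less than about 6 months left.
- Table 2, cumulative: 400 − 174 = 226 entrants after July 2027.

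**The case against.** Four defences deserve weight.

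- **All three sources target 400.** This stands. A reader might infer that the calendars imply different sample sizes, but 24 × 17 = 408, 60 + 340 = 400, and Table 2 reaches 400 on either reading. What differs is when, and at what rate.
- **Table 2 has an innocent reading.** Taken quarterly, its first eight columns sum to 500 referred, 400 recruited and 40 withdrawn, the trial totals. The last three columns may be leftover or cumulative figures. A reader might conclude that 226 participants are randomised after therapy ends, but that depends wholly on the cumulative reading. Even then, only January 2028 entrants would reach month 6 after the June 2028 analysis date.
- **Course length is flexible.** The Intervention section calls its stage timings guidelines and says time to completion varies. It would be too strong to say that late entrants under the Timeline cannot receive MDFT. They could start; some may not complete a typical course before the stated end.
- **The June 2026 transition review covers recruitment and consent.** Appendix II sets criteria for both, so the approach number may be revised. The review does not reconcile the dates.

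A reader might also apply the text's 24 per month to the Timeline's 11 months, reaching 60 + 264 = 324 randomised and a much larger power loss. The documents do not support that: 24 per month was derived for 17 months, and the Timeline sets its own target of 340 in 11.

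**Conclusion.** The point holds in two parts.

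First, the approach number is wrong as written: 500, not 480, at the stated consent rate. Taken alone this is modest, 16 to 19 fewer randomised and about two points of power. It assumes 80% consent and 10% loss exactly as the Protocol does. The text's own 24 per month would avoid the shortfall only at about 86% consent.

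Second, the sample size text and the Timeline cannot both be followed, and Table 2 matches neither. This is the larger matter. Only the text's calendar leaves about six months before the stated end of delivery, and at its stated approach rate and 80% consent it falls short of 400. Under the Timeline, about 31% of the MDFT arm enters with less than about 6 months left, and about 31 of those participants with less than about 4. The resulting dilution cannot be sized, because the Protocol does not say what happens to families still in therapy at the end of July 2027.

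The unadjusted 480 is a minor slip with no consequence for the design.

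**What to change.** 1. Adopt one recruitment calendar and make the sample size text, Table 2 and Timeline agree on start, end, any pause after the pilot, and monthly rate.
2. Reconcile the last randomisation date with the stated delivery end date and typical course length. Which of these changes is for the sponsor and delivery partner to decide.
3. State 500 eligible young people approached, with a rate that fits the chosen window at 80% consent: about 30 per month over 17 months (500/17 = 29.4), or, on the Timeline's efficacy window, about 39 per month (340/0.8 = 425; 425/11 = 38.6).
4. Label Table 2 as quarterly or cumulative and correct the columns that do not fit.
5. Replace the unadjusted 480 followed up with about 432 to 434.

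The edits are to text and one table, and 364 and 400 stay as they are. The cost is a less favourable monthly approach target and a decision on dates, both best settled before efficacy recruitment opens.
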